## 6.2.2 Exclusion Criteria

A patient will be excluded from the Double-blind Phase of the study if any of the following criteria are met:

1. Known noncompliance with dialysis treatment that in the opinion of the Investigator would impede completion or validity of the study;
2. Scheduled to receive a kidney transplant during the study;
3. Known history of allergic reaction to opiates, such as hives (Note: side effects related to the use of opioids, such as constipation or nausea, would not exclude patients from the study);
4. Has a concomitant disease or a history of any medical condition that, in the opinion of the Investigator, could pose undue risk to the patient, impede completion of the study procedures, or would compromise the validity of the study measurements, including, but not limited to:
  - a. Known or suspected history of alcohol, narcotic, or other drug abuse, or substance dependence within 12 months prior to screening;
  - b. Significant systolic or diastolic heart failure (eg, New York Heart Association Class IV congestive heart failure [[Appendix 1, Section 14.1](#)]);
  - c. Severe mental illness or cognitive impairment (eg, dementia);
  - d. Any other relevant acute or chronic medical or neuropsychiatric condition within 3 months prior to screening (eg, diagnosis of encephalopathy, coma, delirium);
5. New or change of treatment received for itch including antihistamines and corticosteroids (oral, IV, or topical) within 14 days prior to screening;
6. New or change of prescription for opioids, gabapentin, or pregabalin within 14 days prior to screening;
7. Received another investigational drug within 30 days prior to the start of screening or is planning to participate in another clinical study while enrolled in this study;
8. In the opinion of the Investigator has pruritus attributed to a cause other than ESRD or its complications (eg, patients with concomitant pruritic dermatological disease or cholestatic liver disease) (Note: Patients whose pruritus is attributed to ESRD complications, such as hyperparathyroidism, hyperphosphatemia, anemia, or the dialysis procedure or prescription may be enrolled);
9. Has localized itch restricted to the palms of the hands;
10. Has pruritus only during the dialysis session (by patient report);
11. Is receiving ongoing ultraviolet B and anticipates receiving such treatment during the study;
12. Participated in a previous clinical study with CR845.

---

**A patient will be excluded from the Open-label Extension Phase of the study if any of the additional following criteria are met at the time of entry into the Open-label Extension Phase:**

13. Completed the Double-blind Phase of this study but exhibited adverse events during the course of the Treatment Period that may preclude continued exposure to the study drug;
14. Was noncompliant with protocol procedures during the Double-blind Phase of this study which is indicative of an inability to follow protocol procedures;
15. Has developed a concomitant disease or any medical condition that, in the opinion of the Investigator, could pose undue risk to the patient, impede completion of the study procedures, or would compromise the validity of the study measurements.

### **6.3 Removal of Patients from Therapy or Assessment**

#### **6.3.1 Discontinuation of Individual Patients**

A patient may withdraw from the study at any time at his/her own request for any reason without prejudice to future medical care by the physician or at the institution.

A patient may be withdrawn at any time due to the following reasons:

1. At the discretion of the Investigator or the Sponsor for safety, behavioral, compliance, or administrative reasons, including, but not limited to:
  - a. Lost to follow-up;
  - b. Adverse event;
  - c. Lack of therapeutic efficacy;
  - d. Pregnancy;
  - e. Eligibility (Inclusion/exclusion criteria);
  - f. Subject non-compliance;
  - g. Subject withdrew consent.
2. If a patient misses 3 consecutive doses either on Week 11 or Week 12 of the Double-blind Treatment Period (these patients may still be eligible for the Open-label Extension Phase at the discretion of the Investigator in consultation with the Sponsor).
3. If patient misses 6 consecutive doses at any time during the Double-blind Treatment Period (these patients may still be eligible for the Open-label Extension Phase at the discretion of the Investigator in consultation with the Sponsor).
4. At the discretion of the Sponsor/Medical Monitor, if a patient receives a prohibited concomitant medication according to [Table 1](#).

- 
5. Any patient who becomes pregnant during treatment must be withdrawn from the study (see [Section 6.5.4.7](#)).

Whenever possible, withdrawal of a patient from study drug by the Investigator should be discussed with the Medical Monitor before the patient stops study drug.

If study drug is discontinued, regardless of the reason, an Early Termination Visit should be completed at the first dialysis after the last dose of study drug or, if not feasible during that timeframe, as soon as feasible. If at all possible, a Follow-up Visit is to be completed 7-10 days after the Early Termination Visit.

A patient may withdraw consent from continued participation in the study at any time. Although a patient will not be obliged to give a reason for withdrawing prematurely, the Investigator must make a reasonable effort to obtain the reason while fully respecting the patient's rights. The reason(s) for termination and date of stopping study drug must be recorded on the electronic case report form (eCRF) and source documents.

If a patient discontinues early due to an adverse event, the event will be followed until resolution, the patient returns to baseline status, the condition stabilizes, or the patient is lost to follow-up.

A patient will be considered lost to follow-up when no response is received from the patient after at least 3 documented attempts to contact the patient over a minimum time of 2 weeks by the study site.

If the patient withdraws consent for disclosure of future information, the Sponsor may retain and continue to use any data collected before such a withdrawal of consent.

Patients who discontinue after the administration of the first dose of study drug will not be replaced.

### **6.3.2 Discontinuation or Suspension of Entire Study**

The Sponsor may suspend or terminate the study or part of the study at any time for any reason. Reasons may include the following, among others:

1. Investigators have not been able to enroll patients within a reasonable period of time or according to inclusion/exclusion criteria;
2. The target number of subjects required for the study is enrolled earlier than expected;
3. Unexpected safety concern.

If the study is suspended or terminated, the Sponsor will ensure that applicable regulatory agencies and Institutional Review Boards (IRBs)/Independent Ethics Committees (IECs) are notified, as appropriate.

---

Should the study be closed prematurely, all study materials (eg, completed, partially completed, and blank eCRFs, as well as study drug) must be returned to the Sponsor or destroyed at the site according to instructions which will be provided by the Sponsor, as applicable.

## **6.4 Treatments**

Additional information on the study drug and its preparation, administration, storage, supply, disposition, and accountability can be found in the Pharmacy Section of the Investigator Site File (ISF).

### **6.4.1 Treatments Administered**

The study drug will be dispensed by qualified staff members who have received training on study drug handling and administration and as per local regulations.

Patients will receive IV CR845 at a dose of 0.5 mcg/kg or placebo after each dialysis session, generally 3 times per week for up to 64 weeks (ie, 12 weeks double-blind and 52 weeks open-label) as an IV bolus into the venous line of the dialysis circuit at the end of each dialysis session and may be given either during or after rinse back of the dialysis circuit. If the dose is given after rinse back, following the IV push of study drug the venous line must be flushed with at least 10 mL of normal saline. If the dose is given during rinse back, no additional normal saline is needed to flush the line. If a patient receives additional dialysis during a given week for any reason, an additional dose of CR845 or placebo will be administered following dialysis. A maximum of 4 doses per week is allowed. No additional doses will be given for patients receiving an additional unscheduled ultrafiltration treatment.

The patient's prescription dry body weight (ie, the target post-dialysis weight, as determined by the patient's nephrologist or dialysis unit during screening) will be used to calculate the dose of the study drug to be administered throughout the Double-blind Treatment Period.

During the Open-label Extension Phase, the patient's current prescription target dry body weight should be compared to the screening dry body weight. If the difference is less than  $\pm 10\%$ , then continue dosing based on the patient's dry body weight recorded at screening. If the difference is  $\pm 10\%$  or more, use the patient's newly recorded dry body weight to calculate the volume of CR845 to be administered. Dosing will be adjusted every 12-weeks if prescription dry body weight changes by  $\pm 10\%$  or more from dry body weight recorded at screening.

### **6.4.2 Identity of Investigational Product(s)**

#### **6.4.2.1 Formulation of Study Drug**

Study drug will be supplied by the Sponsor as a solution in 2-mL glass vials containing a minimum extractable volume of 1.3 mL of CR845 at a concentration of 0.05 mg/mL in

---

0.04 M isotonic acetate buffer, pH 4.5. The composition of the CR845 solution is CR845 (free base), acetic acid, sodium acetate trihydrate, sodium chloride, hydrochloric acid, and water for injection.

Matching placebo (0.04M isotonic acetate buffer, pH 4.5) will be provided in 2-mL glass vials containing a minimum extractable volume of 1.3 mL. The composition of the placebo buffer solution is acetic acid, sodium acetate trihydrate, sodium chloride, hydrochloric acid, and water for injection. The placebo buffer is identical to the buffer solution used in the CR845 solution and has identical appearance as the solution containing the active ingredient. The placebo buffer solution will be packaged, stored, and shipped identically to the CR845 solution.

#### **6.4.2.2 Packaging, Labeling, and Storage Stability of Study Drug**

Study drug will be shipped at 15°C to 30°C. Temperature will be monitored during shipment and verified and recorded in the pharmacy log by the pharmacist upon arrival at the site. The vials must be stored at a temperature ranging from 15°C to 30°C upon receipt and the temperature will be monitored accordingly.

For the Double-blind Treatment Period vials will be packaged (blinded) in boxed kits (also blinded) containing 40 vials per box (4 extra vials for backup). Kits will be labeled with patient ID number and kit number. A single box of vials will be assigned to a patient.

For the Open-label Extension Phase, vials will be packaged in boxed kits containing 12 vials per box. Kits will be labeled with patient ID number and kit number. A single box of vials will be assigned to a patient.

Labeling of the vials and kits will conform to the regulations required by each country.

#### **6.4.2.3 Individual Dose Labeling**

One syringe will be prepared for each patient on each dosing day. Syringes and syringe labels will be provided. Refer to the ISF for details.

#### **6.4.3 Drug Accountability**

All supplies will be maintained under adequate security by the pharmacist or approved staff at the investigational site. At the end of each injection, the used vials will be stored until the study monitor performs accountability. Details of study drug accountability and return are provided in the ISF.

The Sponsor (or delegated person) will be permitted, at intervals and upon request during the study, to check the supplies, storage and dispensing procedures, and records.

#### **6.4.4 Method of Assigning Patients to Treatment Groups**

Before the start of the study, computer-generated randomization schedules will be prepared. Randomization will be performed using an interactive voice or web response system (IVRS/IWRS). Patients will be randomized in a 1:1 ratio to receive either CR845

---

0.5 mcg/kg IV or matching placebo IV during the Double-blind Treatment Period. Patients will be stratified into 2 strata according to their use or non-use of concomitant medications to treat their itch during the pre-randomization week (Run-in Period) as well as the presence or absence of specific medical conditions. These specific medical conditions include:

- History of fall or fracture (related to fall)
- Confusional state or mental status change or altered mental status or disorientation
- Gait disturbance or movement disorder

All eligible patients will receive CR845 at a dose of 0.5 mcg/kg starting on Day 1 of the Open-label Extension Phase.

#### **6.4.5 Preparation of CR845**

In the Double-blind Phase of the study, a single vial of study drug will be used for each patient. Each patient's prescription dry body weight will not exceed 135.0 kg.

In the Open-label Extension Phase of the study, 1 vial of CR845 will be used for patients with a prescription dry body weight  $\leq 135.0$  kg. For patients with a prescription dry body weight  $>135.0$  kg, 2 vials of CR845 will be used to ensure that the full volume of study drug can be prepared. Further details will be provided in the ISF.

Information on the study drug preparation can be found in the Pharmacy Manual.

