--	---

	
periodically until the Open-label End-of-Treatment or Early Termination Visit. ECGs will be monitored at the Open-label End-of-Treatment or Early Termination Visit.
 
The number and reason(s) for missed dialysis as well as the use of antipruritic medications will be recorded throughout the Open-label Extension Phase.
 
The last dose of open-label study drug will be administered at the last dialysis visit on Week 52, or Early Termination.
 
Follow-up Period
 
A final safety Follow-up Visit will be conducted 7-10 days after the End-of-Treatment Visit of the Double-blind Treatment Period for patients not participating in the Open-label Extension Phase, after the End-of-Treatment Visit of the Open-label Extension Phase, or after the Early Termination Visit during either the Double-blind Treatment Period or the Open-label Extension Phase.

STUDY DRUG	
Study drug will be supplied in glass vials containing an extractable volume of at least 1.3 mL of CR845 at a concentration of 0.05 mg/mL in 0.04M isotonic acetate buffer, pH 4.5.

REFERENCE PRODUCT	
Matching placebo (0.04M isotonic acetate buffer, pH 4.5) will be provided in glass vials containing an extractable volume of at least 1.3 mL.

TREATMENT REGIMENS	
Patients will be administered CR845 0.5 mcg/kg or placebo as a single IV bolus 3 times a week after each dialysis session for 12 weeks during the Double-blind Treatment Period.
 
During the Open-label Treatment Period, patients will be administered CR845 0.5 mcg/kg as a single IV bolus 3 times a week after each dialysis session for up to 52 weeks.

STUDY DURATION	
Double-blind Phase:
 
Screening Period: up to 4 weeks (Screening Visit may occur during Run-in Period at the discretion of Investigator) inclusive of the 7-day Run-in Period
 
Double-blind Treatment Period: 12 weeks
 
Open-label Extension Phase: up to 52 weeks
 
Follow-up Period: 7-10 days
 
Total study duration for a single patient: up to approximately 70 weeks

STUDY ENDPOINTS	
Efficacy Endpoints
 
Primary Efficacy Endpoint
 
 
Proportion of patients achieving at least a 3-point improvement from baseline with respect to the weekly mean of the daily 24-hour Worst Itching Intensity NRS score at Week 12 of the Double-blind Treatment Period
 

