### 6.2.1 Inclusion Criteria

To be eligible for inclusion into the Double-blind Phase of the study, a patient must meet the following criteria:

1. Willing and able to provide written informed consent prior to participating in this study;
2. Able to communicate clearly with the Investigator and staff, able to understand the study procedures, and able and willing to comply with the study requirements, including providing written responses to questionnaires;
3. Male or female between 18 and 85 years of age, inclusive;  
**Note:** Subjects in Korea must be male or female between 19 and 85 years of age, inclusive;
4. Has ESRD and has been on hemodialysis 3 times per week for at least 3 months prior to the start of screening;  
**Note 1:** Patients who require an occasional additional dialysis treatment to manage fluid overload or electrolyte excesses may be enrolled as long as it is anticipated that no more than 1 such treatment will be required in any given week and no more than 4 occasions during the 12-week double-blind period. Patients routinely on 4 dialyses a week will not be eligible.  
**Note 2:** Patients receiving in-home hemodialysis may participate as long as they have switched to in-center hemodialysis at least 2 weeks prior to screening and plan to remain on in-center hemodialysis for the duration of the study.  
**Note 3:** Patients receiving alternate dialysis modalities such as nocturnal dialysis will not be eligible.
5. If female, is not pregnant or nursing during any period of the study;

- 
6. If female:
    - a. Is surgically sterile; or
    - b. Has been amenorrhoeic for at least 1 year and is over the age of 55 years;  
or
    - c. Has a negative serum pregnancy test at screening and agrees to use acceptable contraceptive measures (eg, hormonal contraceptives, barrier with spermicide, intrauterine device, vasectomized partner, or abstinence) from the time of informed consent until 7 days after the last dose of study drug;
  7. If male, agrees not to donate sperm after the first dose of study drug until 7 days after the last dose of study drug, and agrees to use a condom with spermicide or abstain from heterosexual intercourse during the study until 7 days after the last dose of study drug. (Note: No restrictions are required for a vasectomized male provided his vasectomy was performed  $\geq 4$  months prior to screening);
  8. Has a prescription dry body weight between 40.0 and 135.0 kg, inclusive;

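### The stated minimum vial volume guarantees the 0.5 mcg/kg dose from one vial only up to 130.0 kg, but the one-vial limit is set at 135.0 kg

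*Protocol*

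**What the plan says.** The relevant statements are spread over several sections of the protocol.

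- **Dose.** Section 6.4.1: "Patients will receive IV CR845 at a dose of 0.5 mcg/kg or placebo after each dialysis session". The screening prescription dry weight "will be used to calculate the dose of the study drug to be administered throughout the Double-blind Treatment Period".
- **Vial content.** Section 6.4.2.1 describes 2-mL glass vials with a "minimum extractable volume of 1.3 mL of CR845 at a concentration of 0.05 mg/mL". The Synopsis, under Study Drug, agrees: "containing an extractable volume of at least 1.3 mL of CR845". The matching placebo vials carry the same minimum volume.
- **Eligible weight.** Section 6.2.1, criterion 8, repeated in the Synopsis: "Has a prescription dry body weight between 40.0 and 135.0 kg, inclusive".
- **Vials per dose, double-blind phase.** Section 6.4.5: "In the Double-blind Phase of the study, a single vial of study drug will be used for each patient". It adds that no patient will weigh more than 135.0 kg. Section 6.4.2.2 supplies 40 vials per patient kit, so the rule must mean one vial per dose.
- **Vials per dose, open-label phase.** Section 6.4.5 uses one vial up to and including 135.0 kg. Above that weight, "2 vials of CR845 will be used to ensure that the full volume of study drug can be prepared".

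**The concern.** Section 6.4.5 gives the reason for its weight cut-off: above it, a second vial is needed to draw the full volume. That presents 135.0 kg as the weight up to which one vial is enough. The protocol's own volume, concentration and dose put the guaranteed limit lower, so the cut-off does not follow from the figures beside it.

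Sites apply this rule at every dose. A preparation rule should work for any vial that meets the stated specification, including one at the minimum. For patients in the top few kilograms of the eligible range, this one does not assure the intended dose.

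**Working it through.** **Inputs**

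- Dose: 0.5 mcg per kg of prescription dry weight (Section 6.4.1).
- Concentration: 0.05 mg/mL = 50 mcg/mL (Section 6.4.2.1).
- Minimum extractable volume: 1.3 mL (Section 6.4.2.1; Synopsis, Study Drug).
- One-vial weight limit: 135.0 kg (Section 6.4.5, both phases; Section 6.2.1 for eligibility).

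**Step 1: try to reproduce the 135.0 kg limit**

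Guaranteed content = volume × concentration = 1.3 × 50 = 65 mcg.

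Highest weight covered = content / dose per kg = 65 / 0.5 = 130.0 kg.

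The 135.0 kg limit is not reproduced.

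**Step 2: what 135.0 kg requires**

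Amount = 135 × 0.5 = 67.5 mcg.

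Volume = 67.5 / 50 = 1.35 mL.

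Excess over the guaranteed volume = 1.35 − 1.30 = 0.05 mL, or 67.5 − 65 = 2.5 mcg. As a share of the dose, 2.5 / 67.5 = 3.7%.

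**Step 3: the shortfall across the band, if only 1.3 mL can be drawn**

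| Dry weight (kg) | Dose (mcg) | Volume needed (mL) | Shortfall (mL) | Shortfall (%) | Delivered (mcg/kg) |
|---|---|---|---|---|---|
| 130 | 65.0 | 1.30 | 0 | 0 | 0.500 |
| 131 | 65.5 | 1.31 | 0.01 | 0.8 | 0.496 |
| 133 | 66.5 | 1.33 | 0.03 | 2.3 | 0.489 |
| 135 | 67.5 | 1.35 | 0.05 | 3.7 | 0.481 |

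A patient of exactly 130.0 kg is fully covered. The band concerned is above 130.0 kg, up to and including 135.0 kg.

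**Step 4: dependence on the actual fill**

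The protocol gives only a minimum, so the yield of a real vial has to be assumed. Weight covered = volume × 50 / 0.5:

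- 1.30 mL (stated minimum): 130 kg.
- 1.35 mL: 135 kg.
- 2.0 mL (nominal vial size, assuming all of it could be drawn): 200 kg.

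An extra 0.05 mL over the minimum closes the gap.

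**The case against.** The strongest reply is that 1.3 mL is a floor. A reader might infer that one vial cannot supply the dose above 130.0 kg. The documents do not support that: a vial yielding 1.35 mL meets the stated specification and supplies the full dose at 135.0 kg. A 1.3 mL minimum and a 135.0 kg limit can both be true of the real product. This reply stands as far as it goes. It leaves the limit unsupported by the only volume the protocol states.

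A reader might also infer that patients would be under-dosed yet recorded as fully dosed. The protocol does not say so. Section 6.4.7 says only that compliance is documented at the dialysis unit, and Section 8.8.1 lists treatment duration, doses received and doses missed. How a partial volume would be recorded is not stated.

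Three further points can be made for the plan:

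- **Preparation details sit in the Investigator Site File and Pharmacy Manual, which are not at hand.** They may well contain a volume table or a second-vial instruction. They would not remove the mismatch between Sections 6.2.1, 6.4.2.1 and 6.4.5.
- **Each double-blind kit holds 4 backup vials.** Section 6.4.5 still prescribes one vial. Criterion 4 of Section 6.2.1 also allows patients expected to need up to 4 extra dialysis sessions, each followed by a dose under Section 6.4.1. Since 36 + 4 = 40, the spares may all be used that way.
- **In the extension, weight changes of less than 10% leave the dose unchanged.** That rule decides when the dosing weight is updated. It does not allow less than the calculated volume to be drawn. It does show that 3.7% is small by the protocol's own standards, which bears on severity.

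**Conclusion.** The mismatch is real and minor. At the stated minimum volume, one vial assures the dose up to and including 130.0 kg, while the one-vial rule runs to 135.0 kg in both phases. The amount not assured rises from zero at 130.0 kg to 0.05 mL (2.5 mcg, 3.7%) at 135.0 kg, and arises only with vials that yield less than the volume needed.

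This rests on the protocol's dose, concentration and minimum volume, and on reading the single-vial rule as per dose. The protocol gives neither the actual fill nor the weight distribution, so the number of patients affected, if any, cannot be estimated. No effect on blinding is expected, because placebo vials have the same minimum volume, and none on the primary analysis.

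**What to change.** Reconcile four figures: the minimum extractable volume, the concentration, the dose per kg, and the weight up to which one vial is used. They need to agree in the Synopsis (weight criterion and Study Drug), Section 6.2.1, Section 6.4.1, Section 6.4.2.1 and both parts of Section 6.4.5. The pharmacy manual should then be checked against the result. If the vials are known to yield enough for 135.0 kg, stating that volume would be one way to close the gap. Which figure changes is for the sponsor to decide.

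The cost is wording in the protocol and, if needed, the pharmacy manual. No analysis changes.
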